8.2.1.1 ITP bleeding score and platelet response

In addition to the platelet response variables defined in [Section 8.1.1](#) the following variables will also be defined based on a combination of platelet response and information from the ITP bleeding score (these will be referred to as Clinical Response variables). In case rescue medications or prohibited medications potentially affecting platelet counts are taken, only the platelet data up to the start date of rescue medication will be utilized for the summary tables (refer to [Section 8.1.4](#)):

- **Clinical Response:** a Clinical Response is defined as a platelet count $\geq 30 \times 10^9/L$ with at least 2-fold increase from the Baseline value AND absence of bleeding, by visit. This must be confirmed by a second measurement at least 5 days later (to allow for the ± 2 -day visit window), showing a platelet count $\geq 30 \times 10^9/L$ and at least 2-fold increase from the Baseline.
- **Time to Clinical Response** is defined as the time from starting treatment (Day 1) to achievement of Clinical Response. The will be taken as the time to the first platelet assessment (obtained at the same time as the corresponding ITP bleeding score assessment). If the second assessment does not fulfill the required criteria for a clinical response, the subject will be considered as a nonresponder at the respective visits.

- **Duration of Clinical Response:** the duration of Clinical Response is defined as the time between achievement of a Clinical Response to the first time a loss of Clinical Response occurred (defined as platelet count $<30 \times 10^9/L$ or less than 2-fold increase from Baseline OR presence of bleeding). Refer to Section 8.1.1 in case a subject has several clinical responses or the clinical response is maintained until the end of the study".
- **Complete Clinical Response:** a Complete Clinical Response is defined as a platelet count $\geq 100 \times 10^9/L$ AND absence of bleeding, by visit. This must be confirmed by a second measurement at least 5 days later (to allow for the ± 2 -day visit window), showing a platelet count $\geq 100 \times 10^9/L$.
- **Time to Complete Clinical Response:** the time to Complete Clinical Response is defined as the time from starting treatment (Day 1) to achievement of Complete Clinical Response
- **Duration of Complete Clinical Response:** the duration of Complete Clinical Response is defined as the time between achievement of a Complete Clinical Response to the first time a loss of Complete Clinical Response occurred (defined as platelet count $<100 \times 10^9/L$ OR presence of bleeding). Refer to Section 8.1.1 in case a subject has several clinical responses or the clinical response is maintained until the end of the study".
- **No Clinical Response or a loss of clinical response:** the platelet count must be defined as a platelet count $<30 \times 10^9/L$ OR $\geq 30 \times 10^9/L$ WITHOUT at least a 2-fold increase from the Baseline value OR presence of bleeding, by visit. This must be confirmed by a second measurement 1 to 9 days* later, showing a platelet count $<30 \times 10^9/L$ OR $\geq 30 \times 10^9/L$ WITHOUT at least a 2-fold increase from the Baseline value.

For all the above response criteria, the calculation rules included in Section 8.1.1 will apply. In addition the following will be applicable:

- The Clinical Response variables will be assessed only for visits for which both platelet counts and the ITP bleeding score are assessed. The last visit cannot be a clinical response as no confirmation after that is available.
- Absence of bleeding is indicated by Grade 0 for all domains of the SMOG, or a Skin Grade of 0 or 1
- Presence of bleeding is indicated by a Mucosae or Organs Grade of ≥ 1 , or Skin Grade of ≥ 2

*This differs from the published definition (Rodeghiero et al, 2009) which requires 2 platelet measurements 1 day apart to define no response or loss of response. In the current protocol platelet count assessments are not as frequently planned (unless unscheduled measurements are performed), thus it was deemed appropriate to modify the definition above to take into account the schedule of assessments in this study.

As a result the following clinical response variables are not in complete accordance with the guideline:

- Duration of Clinical Response
- Duration of Complete Clinical Response
- No Clinical Response

All response variables described above will be listed by dose arm and subject and summarized by dose arm and visit where appropriate. The responder rates will be tabulated as described in [Section 8.1.3.3](#). Moreover the change in category of bleeding from Baseline will also be presented in shift table at all post-Baseline visits by dose arm. Summary tabulations for Clinical Response by dose arm will be repeated according to past intravenous immunoglobulin medication (Yes/No) and the number of past ITP therapies (≤ 2 / > 2). All analyses described in this section will be performed for the FAS.

In case rescue medications are taken, only the data up to (not including) the start date of rescue medication will be utilized for the summary tables. Listings will contain all the data but a footnote will be included indicating the patients for which some data has been excluded from the summary tables. In case of partial dates, the imputation rules for partial dates described in [Section 4.2.7](#) will be applied.

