- Time to Complete Clinical Response: time from starting treatment to achievement of Complete Clinical Response
- Duration of Complete Clinical Response: measured from achievement of Complete Clinical Response to loss of Complete Clinical Response (loss of Complete Clinical Response defined as platelet count $< 100 \times 10^9/L$ or presence of bleeding)
- No Clinical Response: confirmation of platelet count $< 30 \times 10^9/L$ and less than 2-fold increase from Baseline or presence of bleeding
- Assessment of ITP bleeding score over time at Baseline and at each dosing visit in the Dosing Period and to Day 36, Day 50, Day 64 and Day 85 in the Observation Period in Dose Arm 1, to Day 22, Day 36, Day 50 and Day 71 in the Observation Period in Dose Arm 2, to Day 15, Day 29, Day 43 and Day 64 in the Observation Period in Dose Arm 3 and to Day 8, Day 22, Day 36 and Day 57 in the Observation Period in Dose Arms 4 and 5

- Value and change from Baseline in Neurological Fatigue Index for Multiple Sclerosis (NFI-MS) summary score to Day 36, Day 50, Day 64 and Day 85 in the Observation Period in Dose Arm 1, to Day 22, Day 36, Day 50 and Day 71 in the Observation Period in Dose Arm 2, to Day 15, Day 29, Day 43 and Day 64 in the Observation Period in Dose Arm 3 and to Day 8, Day 22, Day 36 and Day 57 in the Observation Period in Dose Arm 4 and 5

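### Complete Clinical Response needs a second count to start, but its loss has no confirming count at its own threshold, and the note on loss confirmation leaves the rule for its duration unclear (minor)

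*SAP*

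**What the plan says.** All in SAP 8.2.1.1 unless stated; counts are ×10⁹/L.

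- **Start of CCR.** A count of at least 100 with no bleeding. "This must be confirmed by a second measurement at least 5 days later", again at 100 or more.
- **End of CCR.** Duration is "the time between achievement of a Complete Clinical Response to the first time a loss of Complete Clinical Response occurred". Loss is a count below 100 or bleeding, and no second measurement is mentioned. Section 2.2.2 agrees: "measured from achievement of Complete Clinical Response to loss of Complete Clinical Response (loss of Complete Clinical Response defined as platelet count" below 100, or bleeding.
- **The only confirmed-loss rule.** It is headed "No Clinical Response or a loss of clinical response". The criterion is a count below 30, a count of 30 or more without doubling from Baseline, or bleeding. "This must be confirmed by a second measurement 1 to 9 days* later", and the confirming count must also be below 30 or lack the 2-fold increase.
- **The asterisked note on that interval.** It says the published definition was modified because counts are scheduled less often here. It continues: "As a result the following clinical response variables are not in complete accordance with the guideline", and lists Duration of Clinical Response, Duration of CCR and No Clinical Response.
- **Repeat responses.** The CCR bullet refers to 8.1.1, where later response periods are added to the overall duration.
- **Eligible visits.** Clinical Response variables are assessed only where both a platelet count and a bleeding score exist, and the last visit cannot be a response.

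**The concern.** A state that takes two counts to enter can be left on one, so ordinary count variation around 100 shortens its recorded duration. Clinical Response, reported beside it, is protected by a confirmed-loss rule.

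The note adds doubt. It names Duration of CCR as affected by the modified confirmation interval, but no confirmed loss at 100 is written anywhere. One programmer may derive an unconfirmed loss. Another may take the note as a sign that confirmation was meant and look for a rule to apply. The duration summarised by dose arm would then depend on who programmed it.

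**Working it through.** The SAP states no figure that depends on this definition, so there is nothing to reproduce. I compared the rules and then sized the difference.

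**1. Rules side by side**

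| | Clinical Response | CCR |
|---|---|---|
| Start | ≥30 and 2-fold, no bleeding; second count ≥5 days later | ≥100, no bleeding; second count ≥5 days later |
| Loss | <30 or not 2-fold, or bleeding | <100 or bleeding |
| Confirming count for loss | 1 to 9 days later, <30 or not 2-fold | none stated |
| Named in the note | yes | yes |

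**2. Worked subject, Dose Arm 1 (assumed counts, no bleeding).** Bleeding-score visits after Day 1 are Days 8, 15, 22, 29, 36, 50, 64 and 85 (2.2.2). CCR starts on Day 15. All later counts are 120 except one of 95 on Day 50.

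- As written: first period 50 − 15 = 35 days. CCR restarts on Day 64, confirmed on Day 71, adding 85 − 64 = 21. Total 35 + 21 = 56 days.
- With confirmation below 100 (Day 57 count is 120): loss not confirmed, 85 − 15 = 70 days.
- The dip costs 70 − 56 = 14 days, the gap between bleeding-score visits. A dip on Day 64 instead costs 21 days (64 − 15 = 49 against 70), because Day 85 cannot start a new period.
- A parallel Clinical Response subject (Baseline 15, counts 45, one count of 28 on Day 50, 45 on Day 57) keeps 70 days.

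**3. Applying the 30/2-fold rule to CCR.** Baseline 25, a fall from 120 to a steady 60 from Day 50. Since 60 ≥ 30 and 60 ≥ 2 × 25 = 50, the loss is never confirmed: 70 days, against 50 − 15 = 35 under the stated <100 definition.

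**4. Simulation (all settings assumed).** Counts are independent and lognormal around a stable level, with σ = √ln(1 + CV²). There is no bleeding. Counts are on the visits above plus Days 32, 43, 57, 71 and 78; with Baseline that is 14, matching the 14 Arm 1 measurements in 8.1.1. Onset is confirmed by the next count at least 5 days later. Loss is either one count below 100 at a bleeding-score visit, or that count plus a low next count within 9 days. Later periods are added. There were 60,000 subjects per setting; means are over those attaining CCR.

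| Level / CV | Level taken as | P(count <100) | Cumulative days, unconfirmed v confirmed | First period only |
|---|---|---|---|---|
| 130 / 25% | median | 0.14 | 63.9 v 71.6 | 50.5 v 69.5 |
| 130 / 25% | mean | 0.17 | 60.8 v 69.8 | 46.6 v 67.0 |
| 150 / 15% | median | 0.003 | 76.7 v 76.9 | 76.2 v 76.9 |
| 150 / 15% | mean | 0.004 | 76.7 v 76.9 | 76.0 v 76.9 |
| 120 / 35% | median | 0.30 | 49.0 v 60.6 | 35.2 v 55.5 |
| 120 / 35% | mean | 0.36 | 43.6 v 55.3 | 31.3 v 49.9 |

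For example, at a median of 130 and CV 25%, σ = √ln(1.0625) = 0.246 and P = Φ(ln(100/130)/0.246) = Φ(−1.07) = 0.14.

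The cumulative column is the SAP's variable. The gap is about 8 to 9 days in the first setting, essentially nil in the second and about 12 days in the third.

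**The case against.** Four stronger readings are tempting, and the SAP does not support them.

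- **That the note says the confirmation rule governs CCR duration.** It does not. It says three variables depart from the published definition, which by the SAP's own account needs two measurements for loss. An unconfirmed CCR loss departs from that too, so listing it is not false. What remains is that the note gives the modified interval as the reason, and that reason fits CCR only if the rule applies to it.
- **That a fall to a steady 60 would never count as loss.** This means overriding the explicit <100 criterion in both 2.2.2 and 8.2.1.1 with a rule headed for Clinical Response. It shows why that rule cannot simply be borrowed; it is not the natural reading.
- **That one low count ends CCR.** It closes a period; 8.1.1 adds later ones. The first-period gap of about 20 days at 130/25% therefore overstates the effect on the defined variable.
- **That the two durations should be directly comparable.** Their thresholds differ by design, and no test compares them.

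Unconfirmed loss is also the SAP's convention for Response, Complete Response and count ≥50 in 8.1.1, so it could be a deliberate choice for CCR. That is fair. If so, the SAP should say so.

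**Conclusion.** The point holds as a minor one. CCR has a confirmed start and, as written, an unconfirmed loss, and the note on loss confirmation does not fit that text cleanly. The practical effect is a tendency towards shorter CCR durations when counts sit near 100: about 8 to 12 days of mean cumulative duration in the two more variable settings and none of note when counts lie well above 100. The levels, CVs and independence of counts are assumptions without support in the SAP, and they drive the size.

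Duration of CCR is summarised descriptively by dose arm on the Full Analysis Set. The tested platelet variables (maximum increase and time to response, 8.1.3) do not use it, and no sample-size or error-rate statement is affected.

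**What to change.** In 8.2.1.1, add to the CCR loss definition:

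1. A platelet loss must be confirmed by a second count below 100 ×10⁹/L 1 to 9 days later, and is dated at the first low count.
2. The confirming count may come from a platelet-only or unscheduled visit. Otherwise the both-measures restriction could block it, since Arm 1 bleeding-score visits after Day 36 are at least 14 days apart.
3. How a low count at the last visit, which cannot be confirmed, is handled.
4. Whether bleeding alone ends CCR, and whether it needs confirmation. The existing Clinical Response rule accepts bleeding as a criterion but asks only for a confirming platelet count, so it gives no model to copy.

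Limit the 30/2-fold confirming rule to Clinical Response. If unconfirmed CCR loss is intended, state that instead, and either remove Duration of CCR from the note or give its separate reason there.

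The cost is a few sentences and a small programming change. Confirmed durations will be somewhat longer than unconfirmed ones.

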3.2.1.2 Study periods

For each subject the duration of the study is approximately 16 weeks.

- Screening Period: 1 to 28 days
- Dosing Period: 1 to 4 weeks; during the Dosing Period subjects will receive weekly doses of UCB7665 (5 doses of 4mg/kg [QWK] in Dose Arm 1, 3 doses of 7mg/kg [QWK] in Dose Arm 2, 2 doses of 10mg/kg [QWK] in Dose Arm 3, 1 dose of 15mg/kg in Dose Arm 4 and 1 dose of 20mg/kg in Dose Arm 5). The dose regimen may be adapted following review by the DMC
- Observation Period: 8 weeks; a visit will be scheduled 3 days after the final dose (or only dose administration for Dose Arms 4 and 5) and weekly thereafter to collect safety and efficacy data

The end of the study is defined as the date of the last visit of the last subject in the study.

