If the platelet value meets the criterion for a specific response for a second time (following a loss of initial response), the second response period will be added to the overall duration of response. This rule will be applied for any subsequent ‘response periods’. For subject in whom the response is maintained until the end of the study the duration of response will be calculated using the date of the end of study visit as the ‘end of response date’. Any such cases will be flagged in the data listings

- **Complete Response:** a platelet count $\geq 100 \times 10^9/L$, by visit, and at any timepoint during the study
- **‘No’ or ‘Loss of’ Complete Response:** a platelet count $< 100 \times 10^9/L$, by visit.

- Time to Complete Response: the time from starting treatment (Day 1) to achievement of Complete Response
- Platelet Count $\geq 50 \times 10^9/L$, by visit, and at any timepoint during the study
- ‘No’ or ‘Loss of’ Platelet Count $\geq 50 \times 10^9/L$: a platelet count $< 50 \times 10^9/L$, by visit.
- Time to Platelet Count $\geq 50 \times 10^9/L$: the time to Platelet Count $\geq 50 \times 10^9/L$ is defined as the time from starting treatment (Day 1) to achievement of Platelet Count $\geq 50 \times 10^9/L$
- Maximum: the maximum value for platelet count over all visits in the study
- Value and change from Baseline in platelet count over time
- Baseline-corrected AUEC for platelet count calculated from Baseline to the end of study visit for each of the defined dose arms.

For all the above response variables the following rules will apply:

- Both scheduled and unscheduled measurements may be included in the calculation of a response, time to response or duration of response
- The Baseline-corrected AUEC will be calculated according to the following rules:
 - The AUEC will be calculated according to the linear trapezoidal rule using protocol scheduled visits
 - Unscheduled visits will not be included in the calculation
 - No imputation of any missing data will be performed
 - To account for differences in the timing of Baseline samples for each subject the Baseline measurement will be considered as time zero in the calculation
 - The units of the AUEC will be $10^9/L \cdot \text{day}$
 - The measurements at Baseline and at the last visit must be available

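### Loss of Clinical Response can be dated only at visits with a bleeding score, so platelet-only visits cannot end a response, and losses in the last three weeks cannot be confirmed

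*SAP*

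**What the plan says.** - SAP Section 8.2.1.1 restricts the whole family of variables: "The Clinical Response variables will be assessed only for visits for which both platelet counts and the ITP bleeding score are assessed". The family includes Clinical Response, Complete Clinical Response, the time to and duration of each, and no or loss of Clinical Response.
- The same section ends a Clinical Response at the first loss, meaning a count below 30 x 10^9/L "or less than 2-fold increase from Baseline OR presence of bleeding". For Complete Clinical Response the platelet limit is 100 x 10^9/L.
- A loss needs confirmation: "This must be confirmed by a second measurement 1 to 9 days* later, showing a platelet count" that again fails the criterion. No bleeding condition is placed on the confirming measurement.
- A response needs a second qualifying count at least 5 days later, with no upper limit. Onset is the first count, "obtained at the same time as the corresponding ITP bleeding score assessment".
- Section 8.2.1.1 also applies the calculation rules of Section 8.1.1, among them: "Both scheduled and unscheduled measurements may be included in the calculation of a response, time to response or duration of response". A response maintained to the end of the study is closed at the end-of-study visit.
- Section 2.2.2 schedules the bleeding score at Baseline, at each dosing visit, and then, for example, "to Day 8, Day 22, Day 36 and Day 57 in the Observation Period in Dose Arms 4 and 5". Section 3.2.1.2 schedules visits more often: "a visit will be scheduled 3 days after the final dose (or only dose administration for Dose Arms 4 and 5) and weekly thereafter".

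**The concern.** Declaring a Clinical Response needs two facts together, a sufficient count and no bleeding, so tying it to visits with both measurements is sound. Loss is different: a platelet fall is enough, and no bleeding score is needed to see it. Applying the joint-visit restriction to loss means that a count already taken, and already meeting the loss definition, cannot end the response. Duration then no longer runs to the first time that a loss occurred, which is how the section defines it. The imported Section 8.1.1 rule points the other way, so two programmers could report different durations from the same data.

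**Working it through.** **1. Visit counts against the SAP.** Platelet visits = dosing visits + one at last dose +3 days + eight weekly visits (+7 to +56 days).

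- Arm 1: 5 + 1 + 8 = 14
- Arm 2: 3 + 1 + 8 = 12
- Arm 3: 2 + 1 + 8 = 11
- Arms 4 and 5: 1 + 1 + 8 = 10

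The area-under-the-effect-curve rule in Section 8.1.1 states 14, 12, 11 and 9. Arms 1 to 3 agree; Arms 4 and 5 are one short of the schedule. If the uncounted visit is Day 4, nothing below changes, because it precedes the first possible onset in those arms.

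**2. Joint visits after the last dose** (Section 2.2.2, days converted by subtracting the last dosing day).

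- Arm 1 (last dose Day 29): Days 36, 50, 64, 85
- Arm 2 (Day 15): Days 22, 36, 50, 71
- Arm 3 (Day 8): Days 15, 29, 43, 64
- Arms 4 and 5 (Day 1): Days 8, 22, 36, 57

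All give +7, +21, +35 and +56 days. The platelet-only visits are therefore +3, +14, +28, +42 and +49 days in every arm.

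**3. Delay in dating a loss.** Delay = next joint visit minus the first platelet visit that shows the loss.

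| First low count (days after last dose) | +14 | +21 | +28 | +35 | +42 | +49 | +56 |
|---|---|---|---|---|---|---|---|
| Next joint visit | +21 | +21 | +35 | +35 | +56 | +56 | +56 |
| Delay (days) | 7 | 0 | 7 | 0 | 14 | 7 | 0 |

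Mean with equal weights: (7 + 0 + 7 + 0 + 14 + 7 + 0)/7 = 35/7 = 5.0 days, the same in every arm. A low count at +3 days is dated 4 days late where a response can already exist (Arms 1 to 3).

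**4. Confirmation after +35 days.** The only later joint visit is +56 days, the last scheduled visit, with no scheduled count after it. A loss dated there cannot be confirmed 1 to 9 days later.

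Example, Arm 1, no bleeding: response from Day 36, counts qualifying at every visit through Day 71 (+42), below 30 on Day 78 (+49) and Day 85 (+56).

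- By the loss definition: Day 78, confirmed 85 - 78 = 7 days later. Duration 78 - 36 = 42 days.
- By the joint-visit rule: Days 36, 50 and 64 are responses (Day 64 is confirmed by Day 71). Day 85 is low but cannot be confirmed. With no recorded loss, the response is closed at end of study as maintained. Duration 85 - 36 = 49 days, 7 days too long.

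**5. Which visits may confirm.** The SAP does not say. If confirmation also had to fall at a joint visit, a loss could be confirmed only when dated on Days 8, 15, 22 or 29 (Arm 1), Days 8 or 15 (Arm 2) or Day 8 (Arm 3), and never in Arms 4 and 5, where the joint visits after Day 8 are 14, 14 and 21 days apart.

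**The case against.** Several counterarguments have force.

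- **Confirmation is part of the design.** A single low count in a 14-day gap that has recovered by the next joint visit is unconfirmed, so it is properly not a loss. This stands: the delay applies to falls that persist.
- **Platelet-only counts are not simply ignored.** The confirming measurement needs only a platelet count, so such a visit can apparently confirm a loss. It can also leave a response unconfirmed: a Day 8 response in Arms 4 and 5 followed by a low Day 15 may become a nonresponse, not a long response. The SAP does not say whether an unconfirmed response visit ends an earlier response; its count meets no loss criterion. The example in step 4 does not depend on this, because Day 64 is confirmed.
- **Section 8.1.1 already allows all counts.** It does, but the section that imports it also contains the restriction and does not say which prevails. That is a conflict, not a cure.
- **Materiality is limited.** Section 8.1.3.2 plans log-rank tests only for the three platelet-only responses. Clinical Response durations are listed and summarized, the bleeding-score objective is exploratory, and Duration of Response is reported without the joint-visit rule.

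A reader might also infer that the bias is largest in, or favours, the single-dose arms, because platelet-only visits are 5/9 = 56% of post-Baseline platelet visits there and 5/13 = 38% in Arm 1. The documents do not support that. The pattern after the last dose is identical in all arms, and the same rule delays onset, which offsets part of the overstatement. In a simulation without bleeding (assumed exponential onset, mean 5 or 10 days, and exponential duration, mean 14 or 28 days), reading loss at every platelet visit shortened duration by 1.7 to 2.7 days in Arm 1, 3.6 to 3.9 in Arm 2, 3.6 to 4.4 in Arm 3 and 3.1 to 3.6 in Arms 4 and 5. With onset also read at every platelet visit, the net overstatement in Arms 4 and 5 fell to 0.2 to 1.0 days, the smallest of all.

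**Conclusion.** The point holds as a defect of definition. As written, five scheduled platelet visits per subject cannot date a loss that the counts alone establish, and no loss first appearing after +35 days can be both dated and confirmed from scheduled visits.

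Recorded duration is up to 14 days too long. The 5-day average rests on three assumptions: the fall persists, each weekly visit from +14 days is equally likely to show it first, and an unconfirmed response visit does not itself end the response. Leaving out a first low count at +14 days in Arms 4 and 5, where a Day 8 response may go unconfirmed, gives (0 + 7 + 0 + 14 + 7 + 0)/6 = 4.7 days. The failure after +35 days needs none of these assumptions; it follows from the visit schedule and the 1-to-9-day rule. No direction of bias between arms is established. The plan should be corrected, although the affected outputs are descriptive.

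**What to change.** Amend Section 8.2.1.1 as follows:

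1. Limit the joint-visit rule to declaring a Clinical Response or Complete Clinical Response.
2. Date loss at the first central platelet count, at any scheduled or unscheduled visit, or the first scored visit that meets the loss definition.
3. Keep the 1-to-9-day confirmation and state that any platelet visit may confirm. Without this, one isolated dip would end a response.
4. State how a low count at the last visit, which cannot be confirmed, is handled.
5. State that the Section 8.1.1 rule on scheduled and unscheduled measurements applies to loss and duration on these terms.

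The cost is a short text change and a small programming change, using counts already collected. Reported durations become somewhat shorter. Onset stays tied to joint visits, so it can still be dated late while loss is dated promptly; the report should say so when durations are presented.
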